Data analysis:	
For the incident users of Jardiance® (Empagliflozin) and of DPP4i, analysis will be performed using the “as-treated” (AT) approach. This corresponds to censoring individuals who discontinue use of the index drug, i.e. either switch from the index drug to any other of the index drug Jardiance® (Empagliflozin) or DPP-4 inhibitor during follow-up or stop using the index drug.
 
For the assessment of the primary and secondary objectives, the main data analysis will be conducted in two stages:
 
 - Construction of the propensity score (PS) by modelling the exposure Jardiance® (Empagliflozin) vs. DPP-4 inhibitor - Estimation of the effect of exposure to Jardiance® (Empagliflozin) on the ketoacidosis, severe urinary tract infections, volume depletion and dehydration compared to those exposed to DPP-4 inhibitor. 
Additional sensitivity analyses will be performed to validate the robustness of alternative definitions of outcome, exposure, covariates and reduction of bias due to matching.
 
The following estimates and comparison will be generated:
 
 - Crude and adjusted incidence rates of each of the outcomes among Jardiance® (Empagliflozin) new users and among DPP-4 inhibitor new users. Incidence rates will be reported as point estimates (in cases per 1,000 person-years) and 95% confidence intervals (CIs). - Summary IRRs, after adjusting (via stratified Mantel-Haenszel analysis) for propensity score deciles and calendar year, among Empagliflozin new users versus DPP-4 inhibitor new users - Adjusted IRRs for each of the outcomes will be the main effect estimates of interest. Adjusted incidence rates and IRRs will be calculated by weighting the incidence or IRR of each stratum (defined by propensity score decile and calendar year) by the amount of Jardiance® (Empagliflozin) person-time within the stratum - An additional analysis will further stratify the IRRs by categories of insulin use at the index date - Additional sensitivity analyses will be performed to evaluate potential for bias and confounding. 		

Name of company: [REDACTED]			
Name of finished medicinal product: Jardiance®			
Name of active ingredient: Empagliflozin			
Protocol date: 16 Oct 2017	Study number: 1245.149	Version/Revision: 3.0	Version/Revision date: 23 Sep 2019

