9.7.2 Main analysis using stratification

For the incident users of Empagliflozin along with their respective comparators, analysis will be performed using the “as-treated” (AT) approach. This corresponds to censoring individuals who discontinue use of the index drug, i.e. who either switch from the index drug to any other of the index drugs (Empagliflozin or DPP-4 inhibitor) during follow-up or who stop using the index drug. The AT approach is considering index periods.

For each event of interest, ketoacidosis, severe urinary tract infections, volume depletion, and dehydration, crude and adjusted incidence rates per cohort will be described and compared by means of incidence rate ratios (IRR). Incidence rates will be reported as point estimates and 95% confidence intervals (CIs). Crude incidence rates will be adjusted per 1,000 person-years. Per cohort and, where appropriate per stratum and/or subgroup, the number of person-years is the sum of length of index periods of all patients. Time to first event occurrence will be compared by means of hazard ratios and their 95% confidence intervals.

IRRs and hazard ratios are analysed using stratification. Strata are defined by PS quintiles. IRRs are investigated by means of a stratified Mantel-Haenszel analysis, while hazard ratios are investigated by means of a Cox regression, if proportional hazards can be assumed.

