4.4 General Principles

All individual collected and derived data will be listed and described per group by means of summary tables presenting frequency counts and percentages for categorical data and arithmetic means, standard deviations, medians, minimum and maximum values for continuous data.

All statistical tests will be conducted with a two-sided significance level alpha of 0.05 and all analyses will be conducted using SAS statistical analysis software version 9.4 (SAS Institute, Inc., Cary, NC) or later.

Baseline (Visit 1) is defined as the last observation on or before the index date.

Let the *index period* define the time from index date to the end of treatment with either EMPAGLIFLOZIN or DPP-4 inhibitor, and the *follow-up period* the time from index date to the end of observation. The *index period during Ramadan* and the *follow-up period during Ramadan*, respectively, are the subperiods of index and follow-up periods, respectively, that will fall in the months of Ramadan as defined in Table 2-1 above, where June 6th 2019 and May 25th 2020 are assumed as the end of Ramadan for the two study years.

Statistical Analysis Plan (SAP)

Document Date: 17APR2019

Document Version: 1.0 Final

Durations of periods, time spans between visits and other times since the index date will be individually derived in days.

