albuterol, dopamine, dobutamine, terbutaline and ritodrine. However, candidates cannot be considered if unknown or missing in a significant number of patients.

If the p-value of bivariate analysis is lower than 0.25, confounder candidates will be included in an initial multivariate logistic regression model. By backward elimination, or other appropriate methods of model selection, the model will be optimized to yield a final model.

The resulting PS will be described by group by means of a summary table. The distribution of the PS will be plotted for the two treatment groups (EMP, DPP-4 inhibitors) to see whether there are any areas where there is no overlap. The estimates of treatment effect may not be reliable in areas where there is no overlap. The area with overlap is called the common support region. It may be necessary to remove subjects outside of the common support region (e.g. extreme tails of the PS distribution) before analysis.

The effect of the confounders in bivariate testing and in the initial and final models will be described by p-values.

PS-based Analysis

Based on those PS, the main analysis approach is stratification to control for confounders,

The stratification will divide the entire study population into five groups by PS quintiles based on their PS value. Quintiles will be used for analysis if the number of patients are sufficiently balanced per group within strata and if the confounding covariates are balanced. Balance will be reviewed graphically and, depending on the scale of the covariate, by Mantel-Haenszel and other applicable tests of confounding covariates of the final model by strata. If, due to significantly low p-values from Mantel-Haenszel and other applicable tests, the balance based on quintiles is insufficient, the number of strata will be increased. Balance investigations will be repeated and the number of strata further increased until a reasonable degree of balance is achieved. It may also be necessary to remove patients from extreme tails of the PS distribution.

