4.9.1 Analysis of Primary Endpoints

For each of the four target adverse events (DKA, volume depletion, dehydration, serious UTI) the primary endpoints are the incidence rates and times to first occurrence in the index period,

Statistical Analysis Plan (SAP)

Document Date: 17APR2019

Document Version: 1.0 Final

analysed within each PS-based stratum by logistic regression and proportional-hazards Cox regression, respectively. Time to first event occurrence will be compared using hazard ratios and their 95% confidence limits. The assumption of proportional hazards will be tested [Kleinbaum 2012].

Estimates for each stratum and respective variances will be averaged across strata to yield overall weighted estimates considering subclass weights [Austin 2010, Guo 2015].

The statistical analysis models will contain factors and covariates with a potential effect on the outcome. These may include the treatment-confounding candidates listed in section 4.9 above, and will include the season, i.e., the quarter of the calendar year of the index date, and other effects yet to be short-listed. Site may also be included as a candidate variable.

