4.10 Changes From Protocol-Specified Analyses

As planned per protocol, stratified Mantel-Haenszel analysis will be applied to evaluate incidence rates of each of the target AEs. 

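### Read literally, SAP 4.9.1 averages the stratum variances, which makes the standard error of the pooled Cox and logistic estimates about √K times too large (2.24 times for five equal strata)

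*SAP*

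**What the plan says.** SAP 4.9 sets up the strata: "The stratification will divide the entire study population into five groups by PS quintiles based on their PS value". The number is not fixed. If "the balance based on quintiles is insufficient, the number of strata will be increased", and the balance check is then repeated.

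SAP 4.9.1 has incidence rates and times to first occurrence "analysed within each PS-based stratum by logistic regression and proportional-hazards Cox regression, respectively". It then gives the pooling rule: "Estimates for each stratum and respective variances will be averaged across strata to yield overall weighted estimates considering subclass weights". Two methods references follow. There is no formula, the subclass weights are not defined, and the scale of averaging is not named. SAP 4.9.2 analyses the Ramadan endpoints in the same way.

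A second route exists for incidence rates. SAP 4.10 states: "As planned per protocol, stratified Mantel-Haenszel analysis will be applied to evaluate incidence rates of each of the target AEs". Protocol 9.7.2 agrees: "IRRs are investigated by means of a stratified Mantel-Haenszel analysis". For hazard ratios, that protocol section has a Cox regression using strata defined by propensity-score quintiles and mentions no averaging of variances. The protocol abstract names the adjusted incidence rate ratios as the main effect estimates and weights each stratum "by the amount of Jardiance® (Empagliflozin) person-time within the stratum".

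SAP 4.4 sets the error rate: "All statistical tests will be conducted with a two-sided significance level alpha of 0.05".

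**The concern.** In the SAP 4.9.1 sentence one verb, averaged, governs both the stratum estimates and their variances. A programmer who follows it computes Σw_k·b_k for the estimate and Σw_k·V_k for its variance. The first is right. The second is the typical variance of one stratum and not the variance of the pooled result, so it gives no credit for combining K independent strata.

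The sentence is the only pooling rule visible in the SAP for the stratified proportional-hazards outputs (tables 15.22 to 15.25 and their counterparts for the other three outcomes). In a safety study an inflated standard error errs towards finding no difference between the drugs. The error would also grow as more strata are added to improve balance.

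**Working it through.** The documents state no standard error, power, effect size or expected event count. The 1,500 patients are attributed to a regulatory requirement, so there is no figure of the plan to reproduce.

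**Inputs from the documents.** K = 5 strata, which may increase (SAP 4.9); two-sided alpha 0.05 (SAP 4.4). Because quintiles are cut on the whole population, size-based weights would be w_k = 1/5. **Assumed:** event counts, hazard ratios and the split of events between groups.

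**Formulas.** Let b_k be the stratum log ratio, V_k its variance, and Σw_k = 1. The strata are independent, so

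- correct: Var(Σw_k·b_k) = Σw_k²·V_k
- literal: Σw_k·V_k
- standard-error ratio: R = √[Σw_k·V_k / Σw_k²·V_k]

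**Equal weights, w_k = 1/K.** The V_k cancel, so R = √K whatever the stratum variances.

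| K | R |
|---|---|
| 5 | 2.24 |
| 6 | 2.45 |
| 8 | 2.83 |
| 10 | 3.16 |

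**Unequal weights, equal variances, K = 5.** R = 1/√Σw_k².

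- Weights 0.10, 0.15, 0.20, 0.25, 0.30: Σw² = 0.225, R = 2.11
- Weights 0.05, 0.10, 0.20, 0.30, 0.35: Σw² = 0.265, R = 1.94
- Weights 0.40, 0.30, 0.15, 0.10, 0.05: Σw² = 0.285, R = 1.87

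If V_k is inversely proportional to w_k, R returns to 2.24.

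**Simulation check.** Five strata of 150 against 150 patients, log odds ratio per stratum, 4,000 runs per scenario, assumed comparator risks of 5% and 25%. The standard error from Σw_k²·V_k was 0.96 to 1.01 times the empirical standard deviation of the pooled estimate. The one from Σw_k·V_k was 2.15 to 2.26 times it.

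**Effect on tests (K = 5, equal weights).** The literal rule needs a true z of 1.96 × 2.236 = 4.38. The actual two-sided alpha becomes about 0.00001.

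**Effect on an assumed 100 events, 20 per stratum.**

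- Equal split: V_k = 1/10 + 1/10 = 0.20. Correct SE = √(0.20/5) = 0.200; literal SE = √0.20 = 0.447. The 95% limits are the HR multiplied and divided by exp(1.96 × 0.200) = 1.48, against exp(1.96 × 0.447) = 2.40.
- Power for HR 2, equal split: z = 0.693/0.200 = 3.47. Correct power Φ(3.47 − 1.96) = 0.93; literal Φ(3.47 − 4.38) = 0.18.
- Power for HR 2, 1:2 split: V_k = 1/6.67 + 1/13.33 = 0.225, correct SE = 0.212, z = 3.27. Correct power Φ(1.31) = 0.90; literal Φ(−1.11) = 0.13.

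**Other assumed cases, equal split.** HR 3: with 50 events power falls from 0.97 to 0.31; with 100 events from about 1.00 to 0.87; with 200 events it stays near 1.00.

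**The case against.** The strongest reply is that the sentence is loose shorthand for a standard method. It says the pooling takes account of subclass weights and cites two methods references. That is compatible with squared weights in the variance, in which case nothing is inflated. The references cannot be consulted here, the text after the Mantel-Haenszel sentence in SAP 4.10 is blacked out, and section 4.9.3 is not in the public text. This stands: the documents do not prove that the wrong formula will be programmed. It does not remove the point, because the words describe an average and Σw_k²·V_k is not one.

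Three stronger readings are tempting and not supported:

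- **That every primary estimate is affected.** The adjusted incidence rate ratios have a stratified Mantel-Haenszel analysis with its own pooled variance. The rule reaches only the averaged Cox and logistic estimates.
- **That a real harm would be reported as no difference.** That depends on event counts and effect sizes that the documents do not give. Strong effects with many events would still be detected. For ketoacidosis, protocol 9.9 already concedes that patient numbers may be too low, so high starting power cannot be presumed.
- **That ratios will be averaged on the natural scale and so biased upward.** The SAP does not say this. Pairing estimates with their variances fits log-scale regression coefficients at least as well. The scale should be stated, but no bias can be attributed to the plan.

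**Conclusion.** The point holds for the pooled within-stratum Cox and logistic estimates, for all four outcomes and for the Ramadan analyses that copy the method. Followed as written, the rule overstates their standard error by about √K: 2.24 for five equal strata, 1.87 to 2.11 in the illustrated cases with unequal weights and equal variances, and 3.16 for ten equal strata. The intervals would be too wide, and a moderate excess risk could be missed. The power figures rest on assumed events and hazard ratios; the factor √K rests only on equal weights and independent strata. Under the charitable reading the inflation is nil, but the SAP still does not determine the weights, the scale or the variance, so the interval could not be reproduced from it. Both readings call for the same correction.

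**What to change.** Replace the pooling sentence in SAP 4.9.1 with:

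> Stratum log hazard ratios (log odds ratios) are combined as Σw_k·b_k with variance Σw_k²·V_k, where the weights w_k sum to 1; 95% limits are computed on the log scale and exponentiated.

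Then define w_k. Stratum size (n_k/N) and the empagliflozin person-time named in the protocol abstract target different populations, so the two must be reconciled. Also state whether the Mantel-Haenszel rate ratio or the averaged within-stratum estimate is primary for incidence.

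For the hazard ratio, an alternative is one Cox model stratified by propensity-score subclass, in line with protocol 9.7.2. It estimates a common hazard ratio with information-based weights and is not identical to the weighted average, so the SAP should name which is used. It also avoids needing an estimate in every stratum. At an assumed 1% risk, the chance that all ten stratum-by-group cells of 150 patients contain an event is only (1 − 0.99^150)^10 ≈ 8%.

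The cost is a sentence or two in the SAP and a line of code. No new data are needed.

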This study will be carried out in the manner of successive surveys that the investigator will be asked to successively write in the case report forms (e-CRFs) from each subject who was initially administered the drug following the study start date until the requested number of subjects is reached. Number of recruited patients will be comparable in each group within a given timeframe (i.e. each site will ensure to recruit similar number of patients for each group according to assigned blocks of enrolment).

Prior to initiation of the study, a written contract shall be concluded, and this contract shall be executed among BI OPU, CRO with the head of the site or the investigator with his/her consent.

Patients will be managed according to the local practice guidelines. The choice of treatment will be solely at the discretion of the participating physician. Empagliflozin and the comparator DPP-4 inhibitor will be administered according to the approved labels in Saudi Arabia. [R17-3427] Hence there are no additional risks to patients by participating in this PASS.

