4.2 Sample Size Rationale

The sample size of 1,500 patients is based on SFDA requirements. The aim is to achieve comparable group sample sizes of 750 patients each. However given the real-world design of this study this may not be possible.

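### The primary models in SAP 4.9.1 are fitted separately in each propensity-score stratum with an open covariate list, so with few events the pooled ratio may be inestimable or biased in either direction; one stratified common-effect model avoids this

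*SAP*

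**What the plan says.** SAP 4.9 forms the strata: "The stratification will divide the entire study population into five groups by PS quintiles based on their PS value". It allows more strata if balance is poor and sets no upper limit. SAP 4.9.1 then fits logistic and Cox models within each stratum and averages the estimates and variances using subclass weights, which it does not spell out.

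On covariates, SAP 4.9.1 says: "The statistical analysis models will contain factors and covariates with a potential effect on the outcome". The PS candidates and site are optional. Season is mandatory, and the list stays open: the models may include the PS candidates "and will include the season, i.e., the quarter of the calendar year of the index date, and other effects yet to be short-listed". The SAP gives no maximum number of terms, minimum event count, rule for a stratum with no events in one group, or penalised or exact method. SAP 4.9.2 applies the same analysis to the Ramadan period, and SAP 4.9.4 repeats it in subgroups.

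Protocol 9.7.2 is simpler: "Strata are defined by PS quintiles", with a stratified Mantel-Haenszel analysis for the incidence rate ratio (IRR) and Cox regression for the hazard ratio (HR). SAP 4.10 keeps the Mantel-Haenszel analysis; the text after that sentence is blacked out.

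**The concern.** Splitting the data into five or more separate regressions divides an already small number of events. Two different things can then go wrong. A stratum with no event in one group gives no finite treatment estimate, and averaging the remaining strata no longer answers the intended question. A stratum that can be estimated, but with many terms for its events, tends to exaggerate a true effect, and averaging does not remove an error that the strata share.

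The open list is a separate weakness. The SAP is labelled final, yet its primary model is unfinished, and no date is given by which the covariates must be fixed. At stake are the main comparative estimates of a safety study whose outcomes include ketoacidosis, for which protocol 9.9 itself says patient numbers may be low.

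**Working it through.** **Inputs from the documents.** SAP 4.2: "The sample size of 1,500 patients is based on SFDA requirements" and "The aim is to achieve comparable group sample sizes of 750 patients each". The only figure to reproduce is 2 x 750 = 1,500; no event rate, effect size or power is given. Five strata give 1,500 / 5 = 300 patients each, about 150 per group. Follow-up is one year. Protocol 9.2.1 expects about 25 sites, so site as a fixed factor costs 24 parameters.

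**Assumed.** Annual risks of 0.5% to 5%. The only rate in the documents, about 25% in protocol 9.5, is a prevalence for urinary tract infection and other risk factors, not for these outcomes.

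**Step 1: events per stratum and per parameter.** Events = 300 x risk. Parameters = 1 treatment + 3 season = 4, or 4 + 24 = 28 with site. The last column is 1 - (1 - (1 - risk)^150)^10, the chance that at least one of the 10 group-by-stratum cells has no event when both groups have the same risk.

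| Annual risk | Events per stratum | Per parameter, season | Per parameter, season + site | Chance of an empty cell |
|---|---|---|---|---|
| 0.5% | 1.5 | 0.38 | 0.05 | 0.998 |
| 1% | 3 | 0.75 | 0.11 | 0.92 |
| 2% | 6 | 1.5 | 0.21 | 0.39 |
| 5% | 15 | 3.75 | 0.54 | 0.005 |
| 25% | 75 | 18.75 | 2.7 | 0 |

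Ten events per parameter would need a risk of 40/300, about 13%, with season only, and 280/300, about 93%, with site. In Ramadan, 30 days at a constant 2% to 5% per year gives 300 x 0.02 x 30/365 = 0.5 to 300 x 0.05 x 30/365 = 1.2 events per stratum.

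**Step 2: simulation.** 1,500 patients, five strata of 300, share treated 30% to 70% across strata, true odds ratio (OR) 2. Maximum-likelihood logistic models were fitted per stratum, log ORs averaged with equal weights, and inestimable strata dropped; 200 to 250 runs per setting. The 20-covariate row comes from a separate simulation of the same size. Entries are the geometric mean OR by control risk.

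| Analysis | 0.5% | 1% | 2% | 5% |
|---|---|---|---|---|
| Separate models, treatment only | 1.36 | 1.69 | 1.96 | 2.07 |
| Separate models, + season | 1.38 | 1.70 | 1.97 | 2.09 |
| Separate models, + season + 20 covariates | - | - | 2.88 | 2.34 |
| Separate models, + season + 10 covariates + site | - | 2.74 | 3.02 | 2.67 |
| One model, PS stratum + season, common effect | 2.11 | 2.15 | 2.08 | 2.00 |
| Stratified Mantel-Haenszel OR | 2.20 | 2.04 | 2.04 | 2.01 |

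All five strata could be estimated in 18%, 66% and 98% of runs with season only at 1%, 2% and 5%, and in 0%, 6% and 95% with 10 covariates and site. Averages for the long models at 1% therefore depend heavily on which strata drop out and should not be read closely.

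**Step 3: precision.** At 5% control risk, the standard deviation of the log OR was 0.22 for Mantel-Haenszel, 0.25 for separate models with season, and 0.40 with 10 covariates and site. Inverse-variance weights reduced that last model's OR only from 2.67 to 2.37.

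**Step 4: no true effect.** With a true OR of 1, no clear bias appeared where the estimate was reliable: at 5%, 1.03 both with season and with the largest model.

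**The case against.** The strongest reply is that the harmful model is not one the SAP commits to. Season is the only named mandatory term and it is harmless here: 1.96 becomes 1.97 at 2% control risk, and 2.07 becomes 2.09 at 5%. The PS candidates and site are optional, candidates with much missing data are barred, and the remaining effects are to be short-listed. The event rates are assumed. At 25% risk, season only gave 1.98, and even the model with 10 covariates and site gave 2.26. All of this stands. It limits the claim to what the SAP permits.

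Adjustment within strata is also not redundant. A reader might infer that the candidates are already in the PS. SAP 4.9 admits only those with a bivariate p-value below 0.25 and then applies model selection, and season and site are not among its candidates. Nor can entry time be taken as balanced by recruitment. Protocol 9 says "Number of recruited patients will be comparable in each group within a given timeframe", but that is an aim, and SAP 4.2 concedes that comparable group sizes may not be reached.

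A reader might also take protocol 9.7.2 to mean that PS strata are the only control for confounding. The abstract's data-analysis row adjusts for calendar year, and protocol 9.3.2 stratifies by treatment complexity and by calendar time of initiation. A term for time of entry therefore has a basis in the protocol.

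Finally, a covariate-free analysis already exists in SAP 4.10. Its standing relative to SAP 4.9.1 cannot be judged from the visible text, and SAP 4.9.1 still describes the separate stratum models as the analysis of the primary endpoints.

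**Conclusion.** The concern holds as a risk that the SAP leaves open and could cheaply avoid. For control risks of 0.5% to 1% and a true OR of 2, separate fitting pulls the average towards no effect, to about 1.4 and 1.7, with or without season. At 2% to 5%, season and 20 covariates raise it to about 2.3 to 2.9 and widen its spread. One stratified model or Mantel-Haenszel stays between 2.0 and 2.2 throughout.

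These sizes rest on assumed risks, a true OR of 2, equal stratum weights and dropping strata that cannot be estimated. They come from logistic models; the Cox models were not simulated.

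Two stronger readings are not supported. One is that the covariate paragraph always pushes the estimate away from the null: the direction depends on the event rate and the number of terms, and no clear bias appeared when there was no effect. The other is that the covariates will be chosen with outcomes in hand. The SAP is dated 17 April 2019, and protocol section 6 puts the end of data collection in Q4 2020. The documents do not say when the list will be closed, and that omission is the fair criticism.

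**What to change.** In SAP 4.9.1:

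- Replace the separate stratum models and averaging with one analysis stratified by PS stratum with a common treatment effect: stratified Cox for the HR and stratified Mantel-Haenszel for the IRR. This follows protocol 9.7.2.
- Keep calendar time of entry, either in the PS or as a single term in that model, in line with the protocol abstract and protocol 9.3.2.
- Close the covariate list before outcome data by group are reviewed, and limit its length to the pooled event count. At 0.5%, 1%, 2% and 5% that count is 1,500 x risk = 7.5, 15, 30 and 75 events.
- Name a penalised or exact method for sparse events or a group with none. This is needed even after the change: at a 0.2% control risk, Mantel-Haenszel gave a finite estimate in only 74% of runs.
- Put any fuller covariate-adjusted model in one named sensitivity analysis.

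The cost is SAP wording and less programming. Less outcome-model adjustment remains for imbalance within strata, and a common-effect model does not show whether the effect differs between strata. The sensitivity analysis covers the first of these.
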